5 ANALYSIS POPULATIONS

The analysis populations, defined below, will be used to perform the data analyses. In the Dosed Group subjects will be presented according to the dose group they were allocated to. In the Safety, Full Analysis Set/Intent-to Treat Populations, any subjects who received a different dose than they were allocated will be presented according to the dose they actually received.

5.1.1 *Screened Population*

The Screened Population will include all subjects screened for inclusion into the study.

5.1.2 *Dosed Group*

The Dosed Group will include all subjects who take at least one dose of study drug.

5.1.3 *Safety Population*

The Safety Population will include all subjects who take at least one dose of study drug and have one subsequent contact with the Investigator. This population will be used to summarize all safety data.

5.1.4 *Full Analysis Set (FAS)/Intent-to-Treat (ITT) Population*

The Full Analysis Set (FAS)/Intent-to-Treat (ITT) Population will include all subjects who take at least one dose of study drug and have at least one evaluable post-dose PK sample. This population will be used in the PPK analysis.

6 GENERAL CONSIDERATIONS FOR DATA ANALYSIS

Statistical analyses will be performed using SAS® (Version 9.3 or later). All available data will be presented in subject data listings, which will be sorted by dose group, subject identifier and where appropriate, visit number and visit/assessment date.

Listings will contain data for all attended visits whether scheduled or unscheduled and visits will be listed in the order in which they were attended. Tables will only summarise data for the scheduled visits.

Dose groups will be displayed in all output using the following labels:

- Ferric Maltol 7.8 mg bid
- Ferric Maltol 16.6 mg bid
- Ferric Maltol 30 mg bid

6.1 Date Format

Only the actual age will be used in this study. The YYYY-01-01 will be used for the Date of Birth. Partial days will be allowed for the duration of disease.

6.2 Other Data Handling Approaches

Descriptive statistics (n, mean, standard deviation (SD), median, maximum and minimum) will be used to summarise the continuous data. Discrete measures will be summarized using counts and percentages (derived from the number of non-missing observations); the number of non-missing (n) observations will also be presented.

Unless otherwise stated, descriptive statistics showing the mean or median will be displayed to one more decimal place than the original data; the standard deviation will be displayed to two decimal places more than the original data and minimum and maximum values will be displayed to the same number of decimal places as the original data.

All fractional numeric values will be printed with a zero to the left of the decimal point (e.g., 0.12, 0.3 etc.). Percentage values will be printed with one digit to the right of the decimal point (e.g., 52.3%, 8.9% etc.).

Categorical data will be summarized descriptively using frequency counts and corresponding percentages.

7 ANALYSIS OF DISPOSITION AND SUBJECT CHARACTERISTICS

7.1 Disposition and Analysis Populations

Subject disposition will be presented for all subjects in the Screened Population. The number and percentage of subjects who meet each of the following categories will be summarised by dose group and overall, as appropriate:

- Screened;
- Screen success;
- Screen failure and reasons for screen failure;
- Dosed;
- Complete the open-label treatment period; and
- Prematurely discontinue during the open-label treatment period and reasons for study discontinuation.

Subjects who screen fail will be listed detailing date of screen failure and primary reason for screen failure.

The number of subjects in the Screened Population, Dosed Group, Safety Population, and FAS/ITT Population will be tabulated by dose group and overall. A listing of analysis population inclusion will also be provided.

Inclusion/Exclusion criteria deviations will be listed and summarized for the Dosed Group and those excluded from the Screened Population.

All available visit dates will be listed for the Screened Population.

A listing of informed consent will be provided for the Screened Population. This listing will contain the date of informed consent (for the subject and/or parent/guardian) and the protocol version to which informed consent was provided; details of reconsent, as appropriate, will also be included.

Treatment details will be listed for the FAS/ITT Population and will contain, for each subject, details of the stratification variables (gender and age group), date of randomization, randomization number, the dose group the subject was randomised/assigned to ('Planned') and the dose the subject actually received ('Actual'), the date of first dose of study drug and the PK Sampling Group the subject was allocated to.

7.2 Protocol Deviations and Violations

CSR reportable protocol deviation include the following categories:

- Inclusion: Subject enrolled did not meet all inclusion criteria (CRA to specify inclusion criteria not met in eMVR);
- Exclusion: Subject enrolled met exclusion criteria (CRA to specify exclusion criteria met in eMVR);
- Withdrawal Criteria: Patient met one or more withdrawal criteria and continued in the study;

- Subject withdrew informed consent;
- Subject unwilling or unable to comply with protocol requirements;
- Subject became pregnant or was not using a reliable method of birth control, if female and of childbearing potential;
- Subject experienced SAEs judged by the investigator to be related to study drug (Ferric Maltol); or
- Subject used prohibited concomitant medication(s).
- Investigational Product:
 - Subject received incorrect dose of study medication (specify dose and timepoint);
 - Subject was dispensed incorrect dose;
 - Study drug compliance <80% per Patient Dosing Card on V3 Day 10 or IP accountability;
 - Study drug compliance >120% per Patient Dosing Card on V3 Day 10 or IP accountability; or
 - Incorrect data provided for stratification at randomisation (specify data).
- Restricted Concomitant Procedure/Medication Change:
 - Subject initiated drug therapy not permitted per protocol (specify medication and timepoint);
 - Immunosuppressant (specify) not taken at a stable dose 12 weeks prior to randomisation
- Study Procedures:
 - Hematology, chemistry, and iron markers not obtained at appropriate visit(s) (specify visit and marker);
 - PK sample not collected (specify visit, PK schedule group and timepoint(s)); or
 - PK sample collected, but not within assigned timepoints ((specify visit, PK schedule group, timepoint(s) assigned and timepoint(s) collected)
 - Day 10 visit was not performed on day 10 past Day 1 visit exactly.
- Breaches in GCP:
 - Subjects (or legal representative) did not sign Informed Consent and Assent prior to study procedures;
 - Patient (or legal representative) did not sign amendment to Informed Consent and Assent which included new study procedures prior to those procedures being performed.

CSR non-reportable protocol deviations include the following categories:

- SAE reporting: Investigator site did not complete the required SAE information including relevant CRF pages or SAE reporting Form and/or notify/submit report to Medpace within 24 hours;
- Informed consent:

- An error in the Informed Consent and Assent administration occurred (specify);
- The Subjects (or legal representative) did not properly sign or did not date the ICF (specify versions);
- The ICF signed by the subject or legally authorized representative is not in the subject's primary language;
- Incorrect Informed Consent and Assent version signed by the subject (specify ICF/assent version);
- Updated Informed Consent and Assent not signed at the first opportunity following approval (specify updated Informed Consent and Assent version);
- A study procedure or medication administration occurred prior to signing the Informed Consent and Assent;
- A subject received IP or has further visits or data collected AFTER withdrawing consent for participation in the study; or
- Subject was not given full and adequate oral and written information about the nature, purpose, possible risk and benefit of the study.
- Subjects (or legal representative) did not sign Informed Consent and Assent prior to second screening
- Study procedures:
 - Physical exam not completed at visit (specify visit);
 - Physical exam not completed at visit (specify visit);
 - Subject was not at rest for 5 minutes prior to Vital signs (BP and HR) being obtained (specify visit);
 - Urine pregnancy test not completed (specify visit); or
 - Vital signs not completed at visit (specify vital sign and visit).
- Investigational product (other than wrong treatment):
 - Study IP stored outside specified ranges in the protocol;
 - IP storage temperature excursion not reported (specify range and dates);
 - Subject dosed with study medication before all inclusion/exclusion were confirmed (specify criteria not confirmed prior to first dose); or
 - IP dose administration instructions not followed (please specify).
 - Day 9 evening dose missed
- Visit windows: Subject was outside of the visit window (specify # of days) for Screening, Day 1 Treatment and Post-Study Follow-Up visits (specify visit).

Protocol deviations will be summarized with frequency distributions (counts and percentages) by dose group and category for the FAS/ITT population. The denominators for calculating percentages will be based on the number of subjects in the FAS/ITT population for each dose group and overall.

Protocol deviations will be provided within a data listing by subject for each dose group.

7.3 Demographics and Baseline Characteristics

Demographic characteristics (year of birth, age, ethnicity, race and gender) and baseline characteristics (height, weight and BMI) as recorded at the Screening Visit will be summarised by dose group and overall using descriptive statistics for the Safety and ITT/FAS Populations. A demographics and baseline characteristics listings will also be produced for the Screened Population. If the Screening retest is performed, the values of Screening retest will be used as baseline.

A listing of reproductive status will be provided for the female subjects only and will contain details of whether the female is of child bearing potential and the method(s) of contraception.

7.4 Medical History

Medical history (event/diagnosis, start and stop dates and status at end of study) will be presented for the Screened Population. Medical history will be summarised by dose group and overall by System Organ Class and Preferred Term for the Safety Population.

8 PHARMACOKINETIC ANALYSIS

8.1 Analysis Populations

The FAS/ITT Population will be used for the primary endpoint analysis.

8.2 Missing Dosing Information

If dosing information is missing, a patient's pre-dose time will be used to impute dosing time to calculate relative time for post-dosing timepoints.

8.3 Missing concentrations

Missing concentrations related to serum iron, TSAT, transferrin, TIBC, UIBC, and NTBI will not be not imputed or used in the analysis. If the dosing history information for a patient is missing, the sampling for that patient relative to the missing dose will not be included in the analysis.

For maltol and maltol glucuronide assessment, all drug concentration below the quantifiable limit (BQL) are treated as zero. When more than half (>50%) of the values at a single timepoint are BQL, mean and median values are reported as BQL. Standard deviation and %CV are not reported; maximum and minimum values are reported as observed (including BQL). If, as the result of the calculation (eg. dose normalization, descriptive statistics) a concentration value is less than the LLOQ the value should be reported as <LLOQ value.

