3 STUDY ENDPOINTS

3.1 Primary Endpoints

The primary endpoints for the study are pharmacokinetic parameters.

1. Population PK analysis of maltol and maltol glucuronide in plasma from PK samples collected on Day 1 (after first morning dose) and Day 10 (after last morning dose). Parameters to be derived and reported for each Ferric Maltol dose are:
 - C_{max} , $C_{ave(0-6h)}$, $AUC_{(0-6h)}$, and $AUC_{(0-Inf)}$ on Day 1 and Day 10 and ratios of Day 10/Day 1 for these parameters;
 - T_{max} ;
 - Half-life ($t_{1/2}$);
 - Apparent systemic clearance (CL/F); and
 - Apparent volume of distribution (V/F).

Plasma concentrations, including C_{trough} of maltol and maltol glucuronide by time of collection on Day 1 and Day 10 will also be presented.

2. Descriptive and population PK analysis of serum iron and TSAT from PK samples collected on Day 1 and Day 10. Parameters to be derived and reported for each Ferric Maltol dose are:
 - Change from pre-dose (C_{trough}) to maximum post-dose (C_{max}) value for serum iron and TSAT; $C_{ave(0-6h)}$;
 - Pre-dose adjusted Incremental $AUC_{(0-6h)}$ on Day 1 and Day 10 from a population PK analysis approach, and percent change from Day 1 to Day 10; and
 - Apparent systemic clearance (CL/F), apparent volume of distribution (V/F).

Serum iron and TSAT by time of collection on Day 1 and Day 10 will also be presented.

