8.4 Observed Maltol, Maltol Glucuronide, Serum Iron, and TSAT

The observed values for maltol, maltol glucuronide, serum iron, and TSAT will be summarized by dose group and by visit/timepoint for FAS/ITT Population using the flowing descriptive statistics: n (the number of subjects), arithmetic mean, minimum and maximum.

The change from baseline values of serum iron and TSAT will be summarized by dose group for each post-baseline visit/timepoint for FAS/ITT Population using the flowing descriptive statistics: n (the number of subjects), arithmetic mean, median, minimum and maximum.

The observed data for maltol, maltol glucuronide, serum iron, and TSAT will also be listed by dose group for each individual subject for FAS/ITT Population.

For maltol and maltol glucuronide, the mean observed plasma concentrations will be plotted on a linear and semi-logarithmic scale against nominal time range by dose group and visit. Geometric mean observed plasma concentrations will be plotted on a linear scale against nominal time range by dose group and visit. Combined observed plasma concentrations will be plotted on a linear and semi-logarithmic scale against actual timepoint for each dose group and visit.

For serum iron, the mean observed serum concentrations will be plotted on a linear and semi-logarithmic scale against nominal time range by dose group and visit. Combined observed serum concentrations will be plotted on a linear and semi-logarithmic scale against actual timepoint for each dose group and visit. The change of baseline will be plotted similarly.

Mean observed TSAT will be plotted on a linear scale against nominal time range by dose group and visit. Combined observed TSAT will be plotted on a linear scale against actual timepoint for each dose group and visit. The change of baseline will be plotted similarly.

The concentration plots described above will be prepared based on the actual data, if applicable.

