8.5.1 Basic Model Construction

The maltol and maltol glucuronide concentrations will be analysed simultaneously by means of fitting the compartment models to observed concentration data using a population PK (PPK) approach.

Likewise, the serum iron and TSAT concentrations will be analysed. If the PPK modelling for TSAT is not feasible, population PD (PPD) approach may be performed.

Population PK models will be built using a nonlinear mixed effects modelling technique with NONMEM® software. It is planned that the first order conditional estimation with interaction (FOCEI) method will be used for model development. If this is not feasible (i.e. the model will fail to converge), the first order conditional estimation (FOCE) and the first order (FO) method will be used instead.

Different models will be attempted to fit the PK concentration-time data. The models will include, but are not limited to, one-compartment linear model, one-compartment linear model with first order absorption, two-compartment linear mammillary model, two-compartment linear mammillary model with first order absorption, three-compartment linear model, and three-compartment linear model with first order absorption, linear compartment model with zero order absorption or saturable absorption. Furthermore, a nonlinear compartment model may also be tested, if possible.

For each individual model, model stability will be assessed with the following:

- Model parameter estimates not close to a boundary;
- Shrinkage for interindividual variability terms (ETA) and residual unknown variability (EPS) < 30%;
- Condition number (ratio of the largest to the smallest eigenvalues) < 1000; and
- Correlation less than 0.90 between any two parameter estimates.

For the final PPK model, diagnostic plots will be presented and assessed.

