8.5.4 Concentration Prediction and Parameter Derivation

The serum iron, plasma maltol, plasma maltol glucuronide concentration, and TSAT versus time profile on Days 1 and 10 will be predicted for each subject using the individual PK parameters estimates from the final model.

Standard non-compartmental methods (NCA) will be used for the PK parameter calculations based on the predicted concentrations. The Linear Up Log Down method (equivalent to the Linear Up/Log Down option in WinNonlin® Professional) will be used in the computation of AUC.

Maltol and maltol glucuronide:

The following parameters for Day 1 will be derived for each Ferric Maltol dose based on the predicted maltol and maltol glucuronide concentrations, if applicable:

Table 4 Parameters for Maltol and Maltol Glucuronide on Day 1

Parameters	Description
C_{\max}	Maximum plasma concentration directly from data
T_{\max}	Time to reach maximum concentration directly from data
λ_z	Apparent first-order terminal elimination rate constant
$t_{1/2}$	Terminal elimination half-life, calculated as $\ln(2)/\lambda_z$
AUC_{0-6h}	Area under the plasma concentration versus time curve from time zero to 6hr.
$AUC_{0-\infty}$	Area under the plasma concentration versus time curve from time zero extrapolated to infinity time
CL/F	Apparent clearance calculated as Dose/ $AUC_{0-\infty}$
V_z/F	Apparent volume of distribution (as Dose/ $[\lambda_z * AUC_{0-\infty}]$)

The following parameters for Day 10 will be derived for each subject based on the predicted maltol and maltol glucuronide concentrations, if applicable:

Table 5 Parameters for Maltol and Maltol Glucuronide on Day 10

Parameters	Description
Tau	The dosing interval for steady-state data tau=12
C_{max}	Maximum concentration between dose time and dose time + Tau. If not unique, then the first maximum is used.
C_{trough}	Minimum concentration between dose time and dose time + Tau
T_{max}	Time to reach C_{max} during a dosing interval
AUC_{0-6h}	Area under the plasma concentration versus time curve from time zero to 6hr.
AUC_{0-tau}	Area under the plasma concentration versus time curve from time zero to Tau
$C_{ave(0-6h)}$	Average Steady State Plasma Concentration from 0-6h, calculated as AUC_{0-6h} divided by 6
CL_{ss}/F	Apparent clearance calculated as Dose/ AUC_{0-tau}
R_{Cmax}	Accumulation ratio based on maximum concentrations after first dose and last dose, calculated as $C_{maxDay10}/C_{maxDay1}$

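### SAP 8.3 sets every BQL maltol value to zero without excepting the population PK fit, which may bias maltol half-life and V/F; size and sign depend on the unstated LLOQ, error model and absorption rate

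*SAP*

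**What the plan says.** SAP 8.3 comes before both the descriptive section (8.4) and the modelling section (8.5). Its rule is: "For maltol and maltol glucuronide assessment, all drug concentration below the quantifiable limit (BQL) are treated as zero". The next sentence is about display: "When more than half (>50%) of the values at a single timepoint are BQL, mean and median values are reported as BQL". The paragraph before it, on missing values and missing dosing history, also decides which samples are analysed: "the sampling for that patient relative to the missing dose will not be included in the analysis".

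SAP 8.5.1 describes "fitting the compartment models to observed concentration data using a population PK (PPK) approach", with maltol and glucuronide modelled together. It says that the "first order conditional estimation with interaction (FOCEI) method will be used for model development", with FOCE and FO as fallbacks. It gives no BQL method, residual-error model or fitting scale. Neither document gives an LLOQ.

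SAP 3.1 lists half-life and V/F for maltol under "Parameters to be derived and reported for each Ferric Maltol dose are". SAP 8.5.4 derives them from model-predicted profiles. Table 4 gives half-life as "Terminal elimination half-life, calculated as" ln(2)/λz, and Vz/F as dose divided by λz times AUC to infinity.

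**The concern.** A BQL maltol value late after dosing means a concentration somewhere between zero and the LLOQ. Entered as an exact zero in a linear-scale fit, it tells the model that drug has gone when some may remain. Each subject gives only two post-dose samples per day, so late records carry much of the information on the terminal slope. Half-life and V/F both rest on that slope.

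If the fit is on the log scale, zeros cannot be used at all. The modeller would have to drop them or improvise, and the SAP gives no guidance.

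**Working it through.** The plan has no figure to reproduce, so the check asks how often BQL values would occur and what zeros would do to the fit.

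**Inputs from the documents**
- Adult maltol at 30 mg (Protocol 5.4, 12.1): mean Cmax 67.3 ng/mL, median Tmax 1.0 h, mean AUC 136 h·ng/mL, mean half-life 0.8 h; detected from 15 min to 4 h; AUC variability about 27%.
- Protocol 5.4: maltol is back to baseline between 3 and 6 h, and its absorption appeared dose proportional.
- SAP Table 3: pre-dose plus two of five post-dose windows reaching 6 h, on Days 1 and 10; 12 subjects per dose.

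**Assumed, because not given:** LLOQ of 1 to 5 ng/mL; true residual error 20% proportional; 27% variability on V/F as well as CL/F; adult values apply to children.

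**Step 1: when maltol drops below the limit.** Under dose proportionality, a lower dose reaches any limit earlier by 0.8 × log2(dose ratio):
- 16.6 mg: 0.8 × log2(30/16.6) = 0.68 h earlier than 30 mg
- 7.8 mg: 0.8 × log2(30/7.8) = 1.55 h earlier than 30 mg

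If the LLOQ is near the adult 4 h level, maltol is last quantifiable at about 4.0, 3.3 and 2.4 h for 30, 16.6 and 7.8 mg.

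**Step 2: calibrating a curve.** One compartment with first-order absorption, k = ln2/0.8 = 0.866/h:
- ka = 2.51/h matches Cmax 67.3, but Tmax = ln(ka/k)/(ka − k) = 0.65 h.
- ka = 1.15/h matches Tmax 1.0 h, but Cmax = 136 × 0.866 × e^(−0.866) = 49.5 ng/mL.
- ka = 2.51/h with a 0.35 h lag matches both, but allows no maltol before 21 min, whereas it was detected from 15 min.

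The adult means do not lie on one simple curve, so all three were used. With ka 2.51 the 30 mg level at 4 h is 5.6 ng/mL without lag and 7.6 with it.

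**Step 3: simulated trials, ka 2.51 with lag (171 replicates; joint fit 104).** Entries are 30/16.6/7.8 mg. Changes are against the same error model fitted to uncensored data.

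| Zeros in the fit | LLOQ 1 | LLOQ 2 | LLOQ 5 |
|---|---|---|---|
| Post-dose share BQL | 3/5/9% | 5/8/15% | 11/17/30% |
| Half-life, combined error, maltol alone | −5/−5/−7% | −9/−10/−14% | −19/−22/−30% |
| Half-life, combined error, joint with glucuronide | −3/−3/−4% | −5/−6/−9% | −12/−15/−23% |
| Half-life, additive error | −0.3/−0.4/−0.5% | −1.4/−1.8/−2.3% | −8/−10/−13% |
| V/F, combined error, maltol alone | −4/−5/−6% | −8/−9/−12% | −17/−20/−23% |

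The joint fit assumes that glucuronide shares maltol's absorption rate. CL/F moves by at most +4% (+10% at 7.8 mg, LLOQ 5) and AUC(0–6h) by at most −3% (−8% there). Consistency check: V/F is proportional to half-life/AUC, so at 7.8 mg and LLOQ 5 the implied AUC ratio is 0.70/0.77 = 0.91, which agrees with CL/F of 1/0.91 = 1.10.

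**Step 4: separately coded simulation, no lag (16–17 trials per setting).** The reference is a censored likelihood (M3).
- *Combined error, ka 2.51:* half-life with zeros against M3 is 0.79 v 0.83 h (−5%), 0.71 v 0.81 (−12%) and 0.58 v 0.81 (−28%) at LLOQ 1, 2.5 and 5. V/F as a fraction of true is 0.96 v 0.99, 0.84 v 0.99 and 0.75 v 0.97. Both were below M3 in 88–94% of trials.
- *Combined error, ka 1.15, LLOQ 5:* 0.79 v 0.86 h (−8%); V/F 0.95 v 1.05.
- *Additive error:* no consistent sign against M3.
- *Proportional error, ka 1.15:* at LLOQ 5, half-life 1.02 v 0.76 h, with residual SD inflated from 0.19 to 0.52; at LLOQ 2.5, V/F 1.21 v 1.05 of true. Here both rise.
- *Proportional error, ka 2.51, LLOQ 5:* half-life unchanged at 0.80 h; V/F 0.76 v 0.95.

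**Step 5: alternatives, in the Step 3 setting.** M3 with combined error leaves half-life within −0.5% to −2.7%. M3 with additive error is no better than zeros (−9/−11/−14% at LLOQ 5). Omitting BQL records lengthens half-life by 3–6% at LLOQ 1 and 17–27% at LLOQ 5. LLOQ/2 with combined error gives 0 to +10%.

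**The case against.** The strongest reply is that the zero rule was meant for tables only. The rest of its paragraph concerns reporting, SAP 8.5.1 fits observed data (a substituted zero is not observed), and Protocol 12.2.4 rules out imputing missing data, with SAP 14 declaring no change from the protocol. That reading is plausible, but nothing settles it. The rule covers all BQL values, sits ahead of both the descriptive and modelling sections, and is the only BQL instruction a modeller has. Protocol 12.2.4 does not say whether a BQL result counts as missing.

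The second reply is that the figures rest on assumptions. That stands: LLOQ, error model, absorption rate and the use of adult values are all open. The bias was also not compared with the sampling error of half-life under this sparse design. The planned diagnostic plots might show the misfit.

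The third reply is that little depends on it. No hypothesis test uses maltol half-life or V/F, and glucuronide is by far the predominant species in plasma (adult Cmax 4677 against 67.3 ng/mL). That limits the importance, but both parameters are still primary endpoints reported by dose.

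**Conclusion.** The gap is real and worth closing before database lock. Read literally, the SAP puts zeros into the primary-endpoint model, and post-dose BQL maltol values are likely at these doses and times. Under combined error with maltol fitted alone, half-life typically shortens by very roughly 5% at LLOQ 1 ng/mL and 20–30% at 5 ng/mL, with V/F falling too. The effect is smaller in a joint fit or with slower absorption.

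Four stronger readings are not supported:
- *Zeros always shorten half-life and lower V/F.* Under additive error at low LLOQ the effect is near nil, and under proportional error the sign can reverse.
- *A false dose effect would follow.* The simulated shortening does grow as dose falls, but SAP 8.5.4 explores dose proportionality through Cmax and AUCs only, and SAP 8.5.3 does not list dose as a covariate.
- *Phase 3 dose choice is at risk.* Protocol 5.4 reports no clear relation between iron uptake and maltol exposure, and no effect on glucuronide has been shown.
- *Day 10 pre-dose zeros make the bias far larger.* At 12 h, 15 half-lives after dosing, all 36 such records would be BQL on the assumed curve. Entering them gave −28% to −44% under combined error, but with the additive SD at its lower bound, so that size is not relied on. Under additive error it was −2% to −15%.

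**What to change.** - In SAP 8.3, state that zero substitution applies only to descriptive summaries and Day 1 pre-dose values.
- In SAP 8.5.1, treat later BQL records (post-dose and Day 10 pre-dose) as left-censored by M3, adding LAPLACE to the listed estimation methods. State the fitting scale and residual-error model, and check that model with diagnostics, because M3 does not help under a wrong additive error.
- If M3 does not converge, report both an LLOQ/2 run and a run omitting BQL records, and show the resulting range for half-life and V/F. Do not present omission as unbiased.
- State the LLOQ and report the BQL fraction by analyte, dose and sampling window. If the fraction proves very small, the issue largely disappears.

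The cost is SAP wording and a standard NONMEM option, with longer run times and possible convergence trouble on sparse data.
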